5.2.2 Saint George's Respiratory Questionnaire (SGRQ)

The Saint George's Respiratory Questionnaire (SGRQ) [[R96-0686](#)] will be completed at Visit 2 and repeated after 12 weeks of treatment (Visit 4).

The SGRQ measures health status in patients with chronic airflow limitation. It comprises two parts which cover three domains (symptoms, activities and impacts) with scores ranging from 0 (no impairment) to 100 (worst possible). Part 1 produces the Symptom score and Part 2 the Activity and Impacts scores. A Total score is also produced.

[Part 1](#) (Questions 1 to 8), covers the patients' recollection of their symptoms over the past four weeks. It is not designed to be an accurate epidemiological tool; its purpose is to assess the patient's perception of their recent respiratory problems. The original version was validated using a 12-month recall period. More recently a 4-week recall version (appropriately worded) has been validated. This has slightly weaker psychometric properties than the 12-month version and produces marginally lower Symptoms score and Total score.

[Part 2](#) (Sections 1 – 7) addresses the patients' current state (i.e. how they are these days). The Activity score just measures disturbances to patients' daily activity. The Impacts score covers a wide range of disturbances of psycho-social function. Validation studies showed that this component relates in part to respiratory symptoms, but is also correlates quite strongly with exercise performance (6-minute walking test), breathlessness in daily life (MRC breathlessness score) and disturbances of mood (anxiety and depression). The Impacts score is, therefore, the broadest component of the questionnaires, covering the whole range of disturbances that respiratory patients experience in their lives. The results will be reported in the eCRFs

Details of the SGRQ are provided in [Appendix 10.4](#).

The baseline for SGRQ will be the measurement made prior to the first dosing at Visit 2.

5.2.3 COPD health status

The COPD Assessment Test™ (CAT) is a short 8-item questionnaire for assessment and monitoring of COPD health status in routine practice. Its scale is 0-40 (high score = poor health). The CAT questionnaire has the advantage of a reduced-number of items and could be used to assess the effects of inhaled therapies [[P11-08788](#)]. A sample CAT is provided in [Appendix 10.3](#)).

The CAT will be performed at Visits 2 and 4.

The test will be performed according to the "HEALTHCARE PROFESSIONAL USER GUIDE; CATTM; COPD Assessment Test; Expert Guidance on frequently asked questions; Issue 3 February 2012" [[R13-0957](#)] provided in the ISF.

Site staff will check the answered CAT questionnaire for completeness. Site staff must not exercise any influence on the patient's answers.

The patient's answers will be transcribed from the CAT questionnaire into the eCRF. The CAT score is the sum of the values corresponding to the answers in the eight questions.

5.3 ASSESSMENT OF SAFETY

There is no endpoint for safety in a statistical sense in this trial. Instead, safety and tolerability will be assessed in a descriptive way based on:

- Adverse events
- Serious adverse events
- Physical examination

5.3.1 Physical examination

A complete, head-to-toe physical examination will be completed on all patients at Visits 1 and 4 (or EOT visit in case of premature withdrawal). Another Physical Examination should be performed at the follow-up visit (Visit 5) only if relevant findings are found at Visit 4. All abnormal findings at Visit 1 will be recorded in the patients' source documents and on the Baseline Conditions eCRF, if applicable. New abnormal findings or worsening of Baseline Conditions during the trial will be recorded as adverse events on the appropriate eCRF page.

The physical examination will also include measurements of systolic and diastolic blood pressure and pulse rate, which will be measured with the patient seated and after having rested for at least five minutes.

5.3.2 Laboratory parameters

Lab assessments will be performed by the central laboratory service provider.

- An absolute Eosinophil count will be performed at the screening visit (Visit 1) and randomization visit (Visit 2) to confirm stability of eosinophil counts.
- Pregnancy testing - A serum human chorionic gonadotrophin (HCG) test will be performed on all females of child-bearing potential at Visit 1. A urine dip stick pregnancy test will be performed at Visits 2, 4 and 5.

5.3.3 Electrocardiogram

A standard 12-lead electrocardiogram (ECG) will be performed on all patients at the screening visit (Visit 1). The purpose of the screening ECG is to obtain information about the patient's baseline condition that may not have been elicited in obtaining the medical history. Therefore, any significant findings from this examination not associated with a baseline condition are recorded on the Baseline Conditions eCRF page. The ECG will be evaluated by the PI and stored in the patient record.

5.3.4 Other safety parameters

Not applicable for this trial.

5.3.5 Assessment of adverse events

5.3.5.1 Definition of adverse events

Adverse event

An adverse event (AE) is defined as any untoward medical occurrence in a patient or clinical investigation subject administered a medicinal product and which does not necessarily have to have a causal relationship with this treatment.

An AE can therefore be any unfavourable and unintended sign (including an abnormal laboratory finding), symptom, or disease temporally associated with the use of a medicinal product, whether or not considered related to the medicinal product.

Adverse reaction

An adverse reaction is defined as a response to a medicinal product which is noxious and unintended. Response in this context means that a causal relationship between a medicinal product and an adverse event is at least a reasonable possibility. Adverse reactions may arise from use of the product within or outside the terms of the marketing authorisation or from occupational exposure. Conditions of use outside the marketing authorization include off-label use, overdose, misuse, abuse and medication errors.

Serious adverse event

A serious adverse event (SAE) is defined as any AE which:

- results in death,
 - is life-threatening, this refers to an event in which the patient was at risk of death at the time of the event; it does not refer to an event that hypothetically might have caused death if more severe.
 - requires inpatient hospitalisation or
 - prolongation of existing hospitalisation,
 - results in persistent or significant disability or incapacity, or
 - is a congenital anomaly / birth defect,
- or
- is to be deemed serious for any other reason if it is an important medical event when based upon appropriate medical judgment which may jeopardise the patient and may require medical or surgical intervention to prevent one of the other outcomes listed in the above definitions.

Medical and scientific judgement should be exercised in deciding whether other situations should be considered serious reactions, such as important medical events that might not be immediately life threatening or result in death or hospitalisation but might jeopardise the patient or might require intervention to prevent one of the other outcomes listed above. Examples of such events are intensive treatment in an emergency room or at home for allergic bronchospasm, blood dyscrasias or convulsions that do not result in hospitalisation or development of dependency or abuse. Any suspected transmission via a medicinal product of an infectious agent is also considered a serious adverse reaction.

AEs considered “Always Serious”

Cancers of new histology and exacerbations of existing cancer must be reported as a serious event regardless of the duration between discontinuation of the drug and the occurrence of the cancer.

In accordance with the European Medicines Agency initiative on Important Medical Events, Boehringer Ingelheim has set up a list of further AEs, which by their nature, can always be considered to be “serious” even though they may not have met the criteria of an SAE as given above.

The latest list of “Always Serious AEs” can be found in the EDC system.

These events should always be reported as SAEs as described above.

Adverse events of special interest (AESIs)

The term AESI relates to any specific AE that has been identified at the project level as being of particular concern for prospective safety monitoring and safety assessment within this trial, e.g. the potential for AEs based on knowledge from other compounds in the same class. AESI need to be reported to the sponsor's Pharmacovigilance Department within the same timeframe that applies to SAE, please see above.

No AESIs have been defined for this trial.

Intensity of AEs

The intensity of the AE should be judged based on the following:

| | |
|-----------|--|
| Mild: | Awareness of sign(s) or symptom(s) that is/are easily tolerated |
| Moderate: | Enough discomfort to cause interference with usual activity |
| Severe: | Incapacitating or causing inability to work or to perform usual activities |

Causal relationship of AEs

The definition of an adverse reaction implies at least a reasonable possibility of a causal relationship between a suspected medicinal product and an adverse event. An adverse reaction, in contrast to an adverse event, is characterised by the fact that a causal relationship between a medicinal product and an occurrence is suspected.

Medical judgment should be used to determine the relationship, considering all relevant factors, including pattern of reaction, temporal relationship, de-challenge or re-challenge, confounding factors such as concomitant medication, concomitant diseases and relevant history.

Arguments that may suggest that there is a reasonable possibility of a causal relationship could be:

- The event is consistent with the known pharmacology of the drug
- The event is known to be caused by or attributed to the drug class.
- A plausible time to onset of the event relative to the time of drug exposure.
- Evidence that the event is reproducible when the drug is re-introduced
- No medically sound alternative aetiologies that could explain the event (e.g. pre-existing or concomitant diseases, or co-medications).
- The event is typically drug-related and infrequent in the general population not exposed to drugs (e.g. Stevens-Johnson syndrome).
- An indication of dose-response (i.e. greater effect size if the dose is increased, smaller effect size if dose is diminished).

Arguments that may suggest that there is no reasonable possibility of a causal relationship could be:

- No plausible time to onset of the event relative to the time of drug exposure is evident (e.g. pre-treatment cases, diagnosis of cancer or chronic disease within days / weeks of drug administration; an allergic reaction weeks after discontinuation of the drug concerned)
- Continuation of the event despite the withdrawal of the medication, taking into account the pharmacological properties of the compound (e.g. after 5 half-lives). Of note, this criterion may not be applicable to events whose time course is prolonged despite removing the original trigger.

- Additional arguments amongst those stated before, like alternative explanation (e.g. situations where other drugs or underlying diseases appear to provide a more likely explanation for the observed event than the drug concerned).
- Disappearance of the event even though the study drug treatment continues or remains unchanged.

5.3.5.2 Adverse event collection and reporting

AE Collection

The Investigator shall maintain and keep detailed records of all AEs in their patient files. The following must be collected and documented on the appropriate CRF(s) by the Investigator:

- From signing the informed consent onwards through the Residual Effect Period (REP) until individual patient's end of trial:
 - all AEs (serious and non-serious).
- After the individual patient's end of trial:
 - the Investigator does not need to actively monitor the patient for AEs but should only report relevant SAEs of which the Investigator may become aware of.

[figure not shown]

Figure 5.3.5.2: 1 All adverse events

AE reporting to sponsor and timelines

The Investigator must report SAEs, and non-serious AEs which are relevant for the reported SAE, on the BI SAE form via fax immediately (within 24 hours) to the sponsor's unique entry point (country specific contact details will be provided in the ISF). The same timeline applies if follow-up information becomes available. In specific occasions the Investigator could inform the sponsor upfront via telephone. This does not replace the requirement to complete and fax the BI SAE form.

With receipt of any further information to these events, a follow-up SAE form has to be provided. For follow-up information the same rules and timeline apply as for initial information.

Information required

For each AE, the Investigator should provide the information requested on the appropriate CRF pages and the BI SAE form. The Investigator should determine the causal relationship

to the trial medication and any possible interactions between the investigational drug(s) and a Non-Investigational Medicinal Product (NIMP) / Auxiliary Medicinal Product (AMP).

The following should also be recorded as an (S)AE in the CRF and SAE form (if applicable):

- Worsening of the underlying disease or of other pre-existing conditions
- Changes in vital signs, ECG, physical examination and laboratory test results, if they are judged clinically relevant by the Investigator.

If such abnormalities already pre-exist prior trial inclusion they will be considered as baseline conditions.

All (S)AEs, including those persisting after individual patient's end of trial must be followed up until they have resolved, have been sufficiently characterised, or no further information can be obtained.

Pregnancy

In rare cases pregnancy may occur in a clinical trial. Once a patient has been enrolled into this clinical trial and has taken trial medication, the Investigator must report immediately (within 24 hours) a potential drug exposure during pregnancy (DEDP) to the sponsor's unique entry point (country-specific contact details will be provided in the ISF). The Pregnancy Monitoring Form for Studies (Part A) should be used.

The outcome of the pregnancy associated with the drug exposure during pregnancy must be followed up and reported to the sponsor's unique entry point on the Pregnancy Monitoring Form for Studies (Part B).

The ISF will contain the Pregnancy Monitoring Form for Studies (Part A and B).

As pregnancy itself is not to be reported as an AE, in the absence of an accompanying SAE, only the Pregnancy Monitoring Form for Studies and not the SAE form is to be completed. If there is an SAE associated with the pregnancy an SAE form must be completed in addition.

Exemptions to SAE reporting

Not applicable for this trial.

5.3.5.3 COPD Exacerbations

For the purpose of this study, a COPD exacerbation is defined as a complex of lower respiratory events / symptoms (increase or new onset) related to the underlying COPD, with duration of three days or more, requiring prescription of antibiotics and/or systemic steroids and/or hospitalization:

A complex of lower respiratory events is defined as at least two of the following:

- Shortness of breath
- Sputum production (volume)
- Change in sputum color
- Cough
- Wheezing
- Chest tightness

“Onset of exacerbation” will be defined by the onset of first recorded symptom. The “end of Exacerbation” will be decided by the investigator based on clinical judgment.

Exacerbations will be classified as follows:

- Mild: a new prescription of maintenance bronchodilator only
Moderate: patient receiving an exacerbation-related prescription of oral corticosteroids and/ or antibiotic not requiring hospitalization.
Severe: COPD-related hospitalization

5.4 DRUG CONCENTRATION MEASUREMENTS AND PHARMACOKINETICS

Not applicable for this trial.

5.5 ASSESSMENT OF BIOMARKERS

Not applicable for this trial.

5.6 OTHER ASSESSMENTS

Not applicable for this trial.

5.7 APPROPRIATENESS OF MEASUREMENTS

Measurements of efficacy parameters will be consistent with the following generally recognized standards:

Spirometry

Pulmonary function tests are a validated and well established measurement tool for lung function testing. Pulmonary function tests will be conducted at clinic visits using standardised spirometry equipment. FEV₁ is a standard measurement for the assessment of lung function.

Questionnaires

- The SGRQ is a well-established and validated questionnaire for the measurement of health status in patients with chronic airflow limitation.
- The COPD Assessment Test™ (CAT) is a short 8-item questionnaire for assessment and monitoring of COPD health status in routine practice.

6. INVESTIGATIONAL PLAN

6.1 VISIT SCHEDULE

Patients should make every attempt to complete the protocol as specified. Each visit date (with its window) is to be counted from Day 1 (Day 1 = Visit 2 / Randomization). If any visit has to be rescheduled, subsequent visits should follow the original visit date schedule. Additional visits for the purpose of re-testing or AE monitoring may be included as deemed necessary by the investigator. Investigators should encourage patient treatment compliance and adherence to other protocol specific activities. Refer to the [Flow Chart](#) for time windows for the visits. All deviations from the planned visit schedule will be documented. After this, a discussion with the Clinical Monitor should take place.

Following the screening visit (Visit 1) and the required minimum of 4 week screening period, eligible patients will be randomised into the 12-week treatment portion of the trial (Visit 2). Visit 3 will take place after approximately 6 weeks of treatment and Visit 4 will take place after approximately 12 weeks of treatment. Approximately three weeks, i.e. 21 days after completion of the end of treatment period (Visit 4), there will be one post-treatment follow-up visit (Visit 5).

Patients should make every attempt to complete the protocol as specified. Investigators should encourage patient treatment compliance and adherence to all protocol specific activities.

Rescheduling in general

A patient visit may be rescheduled twice within the permitted time window of the scheduled visit date (See Flow Chart) due to the lack of medication washout compliance or no intake of study medication the day preceding Visit 3 and 4.

Rescheduling prior to randomisation

The 4-week screening period (between Visit 1 and Visit 2) may be extended by up to 4 weeks (i.e. total up to 8 weeks or 56 days) for administrative reasons and/or to meet wash-out requirements.

If a patient experiences an upper respiratory tract infection (URTI) between Visit 1 and Visit 2, Visit 2 may be postponed until 4 weeks following recovery from the infection.

Note: Patients who experience a lower respiratory tract infection (LRTI) or symptoms of a COPD exacerbation during screening period (Visits 1-2) are not eligible for randomisation and must be withdrawn (screen failure).

If the screening is extended by more than an additional 4 weeks (but not more than an additional 8 weeks), the safety screening examinations have to be repeated prior to randomisation. The repeat screening examination will include a physical examination, measurement of vital signs (blood pressure and pulse rate), 12-lead ECG and clinical laboratory evaluation (total eosinophil count and pregnancy test). The patient should return for these evaluations within 1 week prior to the re-scheduled randomization visit (Visit 2). All adverse events and concomitant therapies will be recorded. If the screening period cannot

be completed within an extension period of 8 weeks, the patient should be considered a screen failure.

Rescheduling after randomisation

Subsequent visits after randomisation should take place at the originally scheduled dates to assure required treatment.

If rescheduling of visits after randomisation is necessary, the adherence to the correct total daily doses of the Respimat[®] Inhaler and/or Diskus[®] Inhaler must be observed. Reserve medication is dispensed at each treatment visit to avoid intermediate visits.

In case a visit needs to be re-scheduled outside the allowed time window (e.g. in order to meet PFT wash-out requirements following treatment of an acute exacerbation), the CML should be contacted.

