Therefore, both treatment regimens are considered options for long-term therapy of COPD and a comparison of both regimens regarding efficacy and safety is of importance for the future treatment of COPD patients.

Women of childbearing potential may be included in clinical trials for tiotropium+olodaterol (5µg/5µg) fixed dose combination provided appropriate precautions are taken to minimise the probability of becoming pregnant. These precautions include pregnancy testing and use of a highly effective method of birth control. Continued testing and monitoring during the trial should be sufficient to ensure compliance with the measures not to become pregnant during the period of drug exposure (which may exceed the length of the study until the follow-up visit at 21 days after discontinuation of the study medication) [[R10-5669](#)].

The trial design requires that all eligible patients complete a four week baseline/run-in period in which LABAs, LAMAs and ICS are withdrawn prior to randomization. At the Investigator's discretion, Atrovent[®] HFA may be provided to patients who are taking a LAMA previous to trial entry for use during the 4 week run-in period; Boehringer Ingelheim (BI) will provide open-label Atrovent[®] HFA for this purpose.

During the entire course of the trial Boehringer Ingelheim will provide open-label albuterol as PRN rescue medication for all patients who have signed Informed Consent.

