3. DESCRIPTION OF DESIGN AND TRIAL POPULATION

3.1 OVERALL TRIAL DESIGN AND PLAN

This is a randomized, double-blind, double-dummy, active-controlled, multi-center, parallel group, Phase IV study to show superiority in lung function of 12 weeks once daily treatment with orally inhaled tiotropium+olodaterol fixed dose combination (5µg/5µg) delivered by the Respimat[®] inhaler vs. 12 weeks twice daily orally inhaled treatment with fluticasone propionate+salmeterol fixed dose combination (250µg/50µg) delivered by the Diskus[®] inhaler in patients with Chronic Obstructive Pulmonary Disease (COPD).

The study will consist of a screening and run-in period of at least 4 four week duration, a 12-week randomised treatment period and a three week follow up period.

After signing Informed Consent (IC) at Visit 0 and completing an initial screening visit (Visit 1), patients enter a four-week screening (baseline) period to ensure clinical stability (i.e. no exacerbations). Patients who meet all inclusion criteria and do not present with any of the exclusion criteria will be randomised into the 12-week treatment period (at Visit 2) in which they will be assigned randomly to one of two treatments. An interactive response technology (IRT) system will be used for randomisation to treatment in this trial and for allocation of medication to patients throughout the treatment period. Additional clinic visits will be scheduled after 6 and 12 weeks of treatment (Visits 3 and 4). A follow-up visit (Visit 5) will be scheduled approximately three weeks after the last dose of study medication.

Individual patient participation is concluded when the patient has completed the last planned visit. The “last-patient-last-visit-primary-endpoint” is the last scheduled primary endpoint visit at Week 12 completed by the last patient. The end of the trial is defined as “last patient out”, i.e. last scheduled visit completed by the last patient.

All randomised patients who withdraw prematurely are encouraged to have an end of treatment (EOT) visit and a follow-up visit, three weeks after the EOT visit.

Site staff will contact the patients by telephone approximately one to two days prior to scheduled PFT visits (Visits 2, 3 and 4) to remind them of medication washout and any other requirements in preparation for the visit (see [Figure 3.1: 1](#)).

[figure not shown]

Figure 3.1: 1 Study design flow diagram

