4.2.1.3 Additional treatment

Medications allowed to control acute exacerbations as medically necessary during the treatment period:

- PRN albuterol HFA inhalation aerosol (MDI) provided by BI.
- Temporary additions of oral steroids are allowed during the treatment portion of the study. Pulmonary function testing visits should not occur within seven days of the last administered dose of an addition of oral steroids. Pulmonary function testing visits may be postponed up to 14 days to meet this restriction. Subsequent visits will be scheduled according to the patient's regular schedule.
- Temporary additions of theophylline preparations are allowed during the treatment portion of the study. Pulmonary function testing visits should not occur within seven days of the last dose. Pulmonary function testing visits may be postponed up to 14 days to accommodate this restriction. Subsequent visits will be scheduled according to the patient's regular schedule.
- The use of antibiotics is not restricted and may be prescribed as medically necessary for exacerbations and / or infections. If antibiotics are prescribed for a respiratory infection prior to pulmonary function testing visits, the visit will be postponed for at least two days but not more than seven days after the last dose is given. Subsequent visits will be scheduled according to the patient's regular schedule.

Oral steroids, theophylline preparations and antibiotics will not be provided by BI.

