6.2.3 Follow up period and trial completion

For all randomised patients termination of trial medication and trial completion must be recorded on the corresponding eCRFs.

Patients who discontinue treatment prior to the planned [Flow Chart](#) visit schedule will complete EOT visit procedures instead of the planned treatment period visit. They will also have a follow-up visit approximately 21 days after last treatment.

Following the end of the 12 weeks of treatment, patients will be followed up for an additional 21 days. They will be seen at the end of this visit (Visit 5) and adverse events and concomitant therapies will be reviewed and recorded. If the physical examination performed at Visit 4 yields abnormal values representing clinically significant changes from baseline, it will be repeated at the follow-up visit (Visit 5). Any persistently abnormal test must be fully explained by the investigator and follow-up evaluation performed if necessary. Additionally, all (S)AEs that occur within 21 days after a patient terminates trial medication must be reported according to Boehringer Ingelheim SAE procedures.

The sponsor must be consulted on all persistently abnormal tests and (S)AEs until it is agreed that follow-up is no longer necessary.

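### After a Visit 4 postponed by 8 to 14 days, the protocol times Visit 5 in two incompatible ways, and no Visit 5 inside the Day 1 window reaches the end of the 21-day adverse event period

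*Protocol*

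**What the plan says.** **Timing from Day 1.** The first paragraph of Protocol Section 6.1 says "Each visit date (with its window) is to be counted from Day 1 (Day 1 = Visit 2 / Randomization" and adds "If any visit has to be rescheduled, subsequent visits should follow the original visit date schedule". Its later text on rescheduling after randomisation repeats that visits keep their original dates. The Flow Chart puts Visit 4 at Day 84 ±3 and Visit 5 at Day 105 ±7. For oral steroids, Section 4.2.1.3 says "Pulmonary function testing visits may be postponed up to 14 days to meet this restriction" and then "Subsequent visits will be scheduled according to the patient's regular schedule"; it gives the same allowance for theophylline. Visit 4 is the last lung function visit, so after a postponed Visit 4 the only visit left to schedule is Visit 5.

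**Timing from the end of treatment.** The second paragraph of Section 6.1 says that about "21 days after completion of the end of treatment period (Visit 4), there will be one post-treatment follow-up visit (Visit 5". Section 3.1 says "A follow-up visit (Visit 5) will be scheduled approximately three weeks after the last dose of study medication". Section 6.2.3 says "Following the end of the 12 weeks of treatment, patients will be followed up for an additional 21 days". Section 2.3 mentions the same interval in passing ("until the follow-up visit at 21 days after discontinuation of the study medication"), but in a paragraph on pregnancy precautions, so it carries little weight as a scheduling rule.

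**The adverse event period.** The last dose is taken at Visit 4 (Section 4.1.4.1). Section 3.1 ends adverse event documentation 21 days after the last dose. Protocol Section 7.3.4 and SAP Section 6.1 assign events in those 21 days to treatment. Participation ends with the last planned visit (Section 3.1), and active monitoring is not required after the patient's end of trial (Section 5.3.5.2).

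**The concern.** A postponed Visit 4 moves the last dose, and with it the end of the 21-day period, to a later date. The Day 1 rule leaves the Visit 5 window where it was. If the delay is long enough, a site that follows the Day 1 rule exactly will hold the final visit, and close the patient's participation, before the treatment-emergent window has closed. The last days of that window then have no scheduled enquiry.

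An event in those days could go unrecorded. This applies mainly to non-serious events, because relevant serious events that the investigator learns of are still reported after the end of trial. The patients concerned would have had Visit 4 moved because of oral steroids or theophylline given for an acute exacerbation. Two sites with the same late Visit 4 could also schedule Visit 5 on different dates, each with a passage to support it.

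**Working it through.** **Inputs**
- Visit 4: Day 84, window ±3, so Day 81 to 87 (Flow Chart).
- Visit 5: Day 105, window ±7, so Day 98 to 112 (Flow Chart).
- Last dose on the day of Visit 4 (Protocol 4.1.4.1).
- Adverse event period ends 21 days after the last dose (Protocol 3.1, 7.3.4; SAP 6.1).
- Permitted postponement: up to 14 days (Protocol 4.2.1.3).

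**The plan's own figure.** 84 + 21 = 105, so the two timings coincide when Visit 4 is on schedule.

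**Visit 4 inside its window.** The 21 days end between 81 + 21 = Day 102 and 87 + 21 = Day 108. Both lie within Day 98 to 112, so both timings can be met.

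**Visit 4 delayed by d days from Day 84**
- Last dose: Day 84 + d.
- End of the 21 days: Day 105 + d.
- Days from last dose to Visit 5: 14 − d at Day 98, 21 − d at Day 105, 28 − d at Day 112.
- Days without scheduled enquiry: 7 + d at Day 98, d at Day 105, and d − 7 at Day 112 (zero if negative).
- An in-window visit reaches the end only if 105 + d ≤ 112, that is d ≤ 7.

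| Delay d | Last dose | 21 days end | Last dose to Visit 5 at Day 98 / 105 / 112 | Days not covered at Day 98 / 105 / 112 |
|---|---|---|---|---|
| 0 | Day 84 | Day 105 | 14 / 21 / 28 | 7 / 0 / 0 |
| 3 | Day 87 | Day 108 | 11 / 18 / 25 | 10 / 3 / 0 |
| 7 | Day 91 | Day 112 | 7 / 14 / 21 | 14 / 7 / 0 |
| 8 | Day 92 | Day 113 | 6 / 13 / 20 | 15 / 8 / 1 |
| 11 | Day 95 | Day 116 | 3 / 10 / 17 | 18 / 11 / 4 |
| 14 | Day 98 | Day 119 | 0 / 7 / 14 | 21 / 14 / 7 |

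For every delay from 8 to 14 days, no in-window date reaches the end of the period. At 14 days the Visit 5 window opens on the day of Visit 4 itself. Timed from the last dose instead, Visit 5 would fall on Day 113 (d = 8) to Day 119 (d = 14), outside the Flow Chart window.

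**Would changing the anchor be enough?** No. A window of ±7 around day 21 allows a visit on day 21 − 7 = 14, which leaves 7 days without scheduled enquiry.

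**The case against.** The strongest reply is that the protocol can be read so that the conflict disappears. Section 6.1 explains that original dates are held so that patients receive the required treatment, a purpose that does not extend to a post-treatment visit. For patients who stop early, follow-up is timed from the last treatment (6.2.3) or from the end-of-treatment visit (3.1), so Day 105 is already not a universal anchor. The passages specific to Visit 5 could also be taken to override a general counting rule. This stands as an indication of intent. It does not settle the matter, because Section 4.2.1.3 expressly applies the regular schedule to visits after a postponed lung function visit, and none of these passages sets Visit 5 for a patient who completes treatment late.

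A second reply is that adverse event collection follows the 21-day period, whatever the date of Visit 5. Sections 3.1, 5.3.5.2 and 6.2.3 require events through that period to be documented or reported, Section 6.1 allows extra visits for adverse event monitoring, and sites are to contact the local clinical monitor about out-of-window visits. This also stands. A reader might infer that the protocol lets events in the last days go uncollected; the documents do not support that. What is missing is a scheduled contact at which to ask, not the duty to report.

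A third reply is that short coverage is not peculiar to late cases. That is correct. With Visit 4 on Day 84, a Visit 5 on Day 98 leaves 7 days; with Visit 4 on Day 87 it leaves 10. A reader might infer that the risk arises only when Visit 4 is late, and the Flow Chart windows contradict that. Only the absence of any workable in-window date is specific to delays of 8 days or more.

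Last, the passages that time Visit 5 from the end of treatment mostly say approximately. That softens the conflict over the visit date, but not the fixed 21-day period.

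**Conclusion.** The inconsistency is real and minor. After a Visit 4 delayed by 8 to 14 days, the two stated timings for Visit 5 cannot both be met. A site following the Day 1 rule then leaves at least 1 day (delay 8) to at least 7 days (delay 14) of the treatment-emergent period without scheduled enquiry, or 8 to 14 days at the nominal Day 105.

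This rests on measuring the delay from Day 84 and ending the period on the date of last dose plus 21. If the day of the last dose counted as day 1 of the 21, the threshold would be 9 days rather than 8. The documents give no rate of postponement, so the number of patients affected is unknown. Figures 3.1: 1 and 5.3.5.2: 1 were not available, so the finding concerns the text only.

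It would go too far to conclude that the safety comparison is biased or the efficacy result weakened. Safety is descriptive with no hypothesis testing, and the primary endpoint is measured at Visit 4. Nor do the documents establish which timing the sponsor intended.

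**What to change.** Reconcile the Flow Chart and Protocol Sections 3.1, 4.2.1.3, 6.1 and 6.2.3 so that one rule, chosen by the sponsor, governs Visit 5 after a postponed Visit 4. State in the same place that adverse event enquiry runs to the end of the 21-day period the documents already define, either through the timing of Visit 5 or, whenever Visit 5 falls earlier, through a brief adverse event contact. The second part is needed under either anchor, and it also covers an early in-window Visit 5 after an on-schedule Visit 4.

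The cost is a wording change to the protocol and, for some patients, a later Visit 5 or one short contact. No further patients are needed, and the SAP's 21-day window stays as it is.
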